9.2.1 Time Period and Frequency for Collecting AE and SAE Information

The collection of non-serious AE information (with the exception of non-serious AEs related to SARS-CoV-2 infection) should begin at initiation of study treatment until the time points specified in the Schedule of Activities (Section 2). Non-serious AE information should also be collected from the start of a placebo lead-in period or other observational period intended to establish a baseline status for the participants.

Following the participant's written consent to participate in the study, all SAEs, whether related or not related to study treatment, must be collected, including those thought to be associated with protocol-specified procedures.

All SAEs must be collected that occur during the screening period and within 100 days of the last dose of study treatment, except in cases where a study participant has started a new anti-neoplastic therapy. However, any SAE occurring after the start of a new treatment that is suspected to be related to study treatment by the investigator will be reported. For participants randomized/assigned to treatment and never treated with study treatment, SAEs should be collected for 30 days from the date of randomization. If applicable, SAEs must be collected that relate to any later protocol-specified procedure (eg, a follow-up skin biopsy).

The investigator must report any SAE that occurs after these time periods and that is believed to be related to study treatment or protocol-specified procedure.

- Medical occurrences that begin before the start of study treatment but after obtaining informed consent will be recorded on the appropriate section of the eCRF section.
- All SAEs will be recorded and reported to sponsor or designee within 24 hours, as indicated in Appendix 3.
- The investigator will submit any updated SAE data to the sponsor within 24 hours of this being available.

Investigators are not obligated to actively seek AEs or SAEs in former study participants. However, if the investigator learns of any SAE, including a death, at any time after a participant has been discharged from the study, and he/she considers the event reasonably related to the study treatment or study participation, the investigator must promptly notify the sponsor.

The method of evaluating, and assessing causality of AEs and SAEs and the procedures for completing and reporting/transmitting SAE reports are provided in Appendix 3.

All SAEs, and all AEs (SAEs and non-serious AEs) associated with confirmed or suspected SARS-CoV-2 infection must be collected from the date of the participant's written consent until 100 days following discontinuation of dosing.

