On treatment tumor biopsy		X	On-treatment tumor biopsy optional for all participants (see Table 9.8.2.6-1). Biopsied lesions should be distinct from index lesion(s) being evaluated for radiological response, if clinically feasible.
Exploratory Serum & Plasma Biomarkers, Peripheral Blood Mononuclear Cells (PBMCs)		X	Refer to Table 9.8.2.6-1.
Whole Blood Sample (DNA)		X	The whole blood sample (DNA) is to be collected predose for the first dose only (only one time point). See Table 9.8.2.6-1.
Additional Research Sampling		X	See Section 9.8.2.7.
Patient-Reported Outcomes Assessments			
EQ-5D-3L	X		Each assessment should be completed at the start of the clinic visit prior to dosing. Pediatric participants (≥12 and <18 years of age) should only complete the EQ-5D-3L and not the WPAI:GH or FACT-M assessments
FACT-M	X		
WPAI:GH	X		
Health Care Resource Utilization	X		Health care resource utilization data will be collected at each visit by study site staff using the CRF.
Clinical Drug Supplies			
Administer Study Treatment	X		The first dose is to be administered within 3 calendar days following randomization. Study treatments will be administered via a single IV bag in a single 1-hour infusion. Treatment will continue until progression, unacceptable toxicity, or study ends.

^a If a dose is delayed, the procedures scheduled for that same time point should also be delayed to coincide with when that time point's dosing actually occurs, except for body imaging and pregnancy testing.

Table 2-3: Follow-Up Procedural Outline (CA224047)

Procedure	Follow-Up ^a Visits 1 and 2	Survival Follow- Up Visits ^b	Notes
Safety Assessments			
Targeted Physical Examination	X		Weight, BP, heart rate, and temperature. Targeted physical examination to be performed only as clinically indicated.
Serious Adverse Events Assessment / Adverse Events Assessment	X		All SAEs and non-serious AEs should be collected continuously during the treatment period and for a minimum of 100 days following discontinuation of study treatment. Participants will be followed for all SAEs, non-serious AEs of special interest (as defined in Section 9.2.3), and all AEs (SAEs and non-serious AEs) associated with confirmed or suspected SARS-CoV-2 infection until resolution, the condition stabilizes, the event is otherwise explained, the event is deemed irreversible, the participant is lost to follow-up (as defined in Section 8.3), or for suspected cases, until SARS-CoV-2 infection is ruled out.

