This study will consist of three phases: screening, treatment, and follow-up.

Screening Phase:

- Begins by establishing the participant's initial eligibility and signing the informed consent form (ICF).

Treatment Phase:

- Begins with the randomization call to the IRT. The participant is randomly assigned to either the BMS-986213 arm or the nivolumab monotherapy arm.
- Ends when the participant is discontinued from study therapy. For a complete list of reasons for treatment discontinuation, see [Section 8.1](#).

Follow-Up Phase

- Begins when the decision to discontinue a participant from study therapy is made (no further treatment with study therapy) and ends when survival data have been collected for all participants (Section 8.1.3).

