#### **7.1.1.3 Immune-Mediated Adverse Events (US Submission)**

In order to further characterize AEs of special clinical interest analysis of immune-mediated AEs (IMAE) will be conducted. Immune-mediated AEs are specific events (or groups of PTs describing specific events) that include pneumonitis, diarrhea/colitis, hepatitis, nephritis/renal dysfunction, rash, endocrine (adrenal insufficiency, hypothyroidism/thyroiditis, hypothyroidism, thyroiditis, hyperthyroidism, diabetes mellitus, and hypophysitis), and other specific events, considered as potential immune-mediated events by investigator, that meet the definition summarized below:

- those occurring within 100 days of the last dose,

- regardless of causality, treated with immune-modulating medication (of note, endocrine AEs such as adrenal insufficiency, hypothyroidism/thyroiditis, hyperthyroidism, diabetes mellitus, and hypophysitis are considered IMAEs regardless of immune-modulating medication use, since endocrine drug reactions are often managed without immune-modulating medication).
- with no clear alternate etiology based on investigator assessment, or with an immune-mediated component

The list of MedDRA preferred terms used to identify Immune-Mediated adverse events is revisited quarterly and updated accordingly. The preferred terms used for the selection at the time of the database lock by categories will be provided.

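### The protocol both stops and does not stop collecting unrelated SAEs when a new anticancer therapy starts, and the SAP's 100-day safety tables that use these events are not cut at that point

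*Protocol*

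**What the plan says.** Protocol 9.2.1 gives the SAE window as "within 100 days of the last dose of study treatment, except in cases where a study participant has started a new anti-neoplastic therapy". It then keeps one class of event after the switch: "any SAE occurring after the start of a new treatment that is suspected to be related to study treatment" is still to be reported. For non-serious AEs the same section sets no end date of its own; they run "until the time points specified in the Schedule of Activities".

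The closing sentence of 9.2.1 reads differently. "All SAEs, and all AEs (SAEs and non-serious AEs) associated with confirmed or suspected SARS-CoV-2 infection must be collected", it begins, and these "must be collected from the date of the participant's written consent until 100 days following discontinuation of dosing". New therapy is not mentioned.

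Table 2-3, the follow-up part of the Schedule of Activities, says that all SAEs and non-serious AEs should be "collected continuously during the treatment period and for a minimum of 100 days following discontinuation of study treatment". It has no exception for new therapy either. Its footnote times Follow-up Visit 2 at 100 days (± 7) from last dose and recognises that discontinuation may fall more than 42 days after last dose.

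On the analysis side, SAP 6.1 counts AEs within 30 or 100 days of last dose. SAP 7.1.1.3 defines IMAEs as investigator-considered potential immune-mediated events within 100 days of last dose, whatever the causality judgement. Non-endocrine events must have been treated with immune-modulating medication, and an event qualifies "with no clear alternate etiology based on investigator assessment, or with an immune-mediated component". SAP 7.6.5 (all-cause AEs, repeated at 100 days), 7.6.10 (IMAEs) and 7.6.11 (other events of special interest, OEOSI) use the 100-day window. None of these sections mentions a cut at subsequent therapy.

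**The concern.** A site that follows the first rule in 9.2.1 goes on recording non-serious events after next-line therapy starts but stops recording serious ones judged unrelated. That is an odd asymmetry, and it is unlikely to be intended. A site that follows Table 2-3 records both. Whether an unrelated SAE after a switch is in the database therefore depends on which sentence the site read.

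The SAP then uses these events without asking when next-line therapy began. Protocol 5.4.4 names ipilimumab among the active options after progression, so next-line immune toxicity inside the 100 days is foreseeable. Immune-mediated toxicity is central to the benefit-risk case for adding relatlimab (Protocol 3.3), and the IMAE tables are meant for a submission. What is at stake is what those tables measure and how completely they are populated. PFS, OS and ORR are not touched.

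**Working it through.** No figure in the plan needs reproducing. The check is a comparison of passages and some day counting.

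**1. Collection rules side by side**

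| Place | Events | Clock starts | Stop at new therapy |
|---|---|---|---|
| 9.2.1, SAE paragraph | SAEs | last dose | yes, unless suspected related |
| 9.2.1, closing sentence | all SAEs; SARS-CoV-2 AEs | discontinuation of dosing | none |
| Table 2-3 | all SAEs and non-serious AEs | discontinuation of treatment (a minimum) | none |

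The rows agree on related SAEs and disagree on unrelated SAEs after a switch.

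**2. Length of the disputed period.** Count last dose as day 0 and let next-line therapy start on day T. Unrelated SAEs are in dispute for 100 − T days. The documents give no distribution for T, so these values are assumptions:

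- T = 10: 100 − 10 = 90 days
- T = 30: 100 − 30 = 70 days
- T = 60: 100 − 60 = 40 days
- T = 100 or later: 0 days

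The 30-day tables are affected only if T is below 30, and then for 30 − T days (20 days at T = 10).

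**3. Which tables draw on these events**

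- General SAE tables (SAP 7.6.2) and AEs leading to discontinuation (7.6.3) use 30 days only, so they are largely outside the problem.
- The 100-day all-cause AE table (7.6.5) includes serious events and is affected. It shows only events with at least 5% incidence in an arm.
- In 7.6.10, the serious IMAE tables are affected, and so are the other IMAE tables where the event was serious. The first summary there counts every AE on the IMAE term list without any requirement on etiology or immune-modulating treatment, so a next-line event on that list is counted. No drug-related version of the IMAE tables is listed.
- The OEOSI tables (7.6.11) are affected in the all-cause version; a drug-related version is also planned.

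**4. The clock.** Let D be the days from last dose to discontinuation. One clock ends on day 100, the other on day D + 100. D is not given, so again by assumption:

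- D = 0: both end on day 100
- D = 43 (just past the 42 days in the Table 2-3 footnote): day 143
- D = 57 (just over the 8-week, 56-day delay in 8.1.1): day 157

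D cannot be negative, so both clocks cover days 0 to 100 in full. Every SAP window in step 3 ends on or before day 100 from last dose. The extra D days enter none of those tables. The practical loose end is that Follow-up Visit 2 falls on day 93 to 107 and Table 2-3 marks AE assessment at Visits 1 and 2 only. Whenever D exceeds 7, the longer clock runs past the last scheduled AE visit.

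**The case against.** The best defence has four parts.

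- **The closing sentence of 9.2.1 came in with the SARS-CoV-2 text and can be read as limited to it.** Possibly, but as written it covers all SAEs, and Table 2-3 conflicts with the SAE paragraph without its help. Nor does the detailed paragraph plainly outrank the schedule: 9.2.1 sends non-serious AEs there, and Section 9 makes adherence to the schedule a requirement.
- **The gap is narrow.** This stands. Related SAEs are reported on every reading, and the general SAE tables stop at 30 days.
- **Counting everything to 100 days is a coherent safety convention that catches delayed immune toxicity.** This also stands, and it is why the uncut tables should stay. It does not supply a way to see how much of the count follows a switch.
- **It is late.** By SAP version 5.0 the primary analysis had been done and subjects unblinded, so new cuts would be post hoc and uncollected events stay uncollected. True; the added tables should be labelled accordingly.

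Three stronger readings are tempting and are not supported.

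- A reader might infer that the two clocks make ascertainment inconsistent within the 100 days, or that a 57-day gap changes the reported rates. Step 4 of the working shows that neither follows. Section 9 says that the Follow-Up Phase "Begins when the decision to discontinue a participant from study therapy is made", but that defines a phase and sets no AE clock.
- A reader might infer from the planning medians (6.9 and 11.8 months) that control participants switch sooner and that next-line events would hide an excess on the combination. Contamination depends on the interval from each participant's own last dose to next therapy and on who has stopped by the cutoff. Stopping for toxicity and treatment beyond progression (8.1.2) also enter. The documents quantify none of this.
- A reader might say that colitis under next-line ipilimumab certainly qualifies as an IMAE. The alternative wording in SAP 7.1.1.3 makes that arguable, not settled, since the investigator's view of etiology is part of the definition.

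**Conclusion.** The conflict is real and sits in current text. For unrelated SAEs after a switch to new anticancer therapy within 100 days of last dose, the protocol gives sites two incompatible instructions, and the SAP's 100-day all-cause AE, IMAE and OEOSI summaries use those events uncut. The rates can therefore combine study-drug and next-line toxicity, with capture of the serious unrelated part varying by site.

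The disputed period is 100 − T days per affected participant, 70 days if T is 30; T is assumed. The number of participants, and the size and direction of any difference between arms, cannot be determined from the documents. The last-dose versus discontinuation wording is a secondary inconsistency that matters only after day 100. This is worth correcting because it bears on what the safety tables can conclude. It does not threaten the efficacy analyses.

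**What to change.** **Protocol.** Reconcile Table 2-3, the SAE paragraph of 9.2.1 and the closing sentence of 9.2.1 so that all three give one clock and one statement on new therapy. The sponsor should decide which, and should say whether the closing sentence is meant for all SAEs or for SARS-CoV-2 events only.

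**SAP.** In 7.1.1.3, 7.6.10 and 7.6.11, add 100-day IMAE and OEOSI summaries cut at the start of subsequent systemic anticancer therapy, alongside the uncut ones. The start dates are already needed for PFS censoring (4.1.1.1), and subsequent systemic therapy is already listed by subject (7.4.3.2).

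**Cost.** A protocol clarification, a few lines of SAP text and a few repeat tables. Delayed study-drug events that appear after a switch will show only in the uncut version, so both versions are needed. Events that sites did not collect in the past cannot be recovered, and the report should say so.

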9.2.2 Method of Detecting AEs and SAEs

Adverse events can be spontaneously reported or elicited during open-ended questioning, examination, or evaluation of a participant. Care should be taken not to introduce bias when collecting AE and/or SAEs. Inquiry about specific AEs should be guided by clinical judgement in the context of known adverse events, when appropriate for the program or protocol.

Every adverse event must be assessed by the investigator with regard to whether it is considered immune-mediated. For events which are potentially immune-mediated, additional information will be collected on the participant's case report form.

9.2.3 Follow-up of AEs and SAEs

- Non-serious AEs should be followed to resolution or stabilization, or reported as SAEs if they become serious (see [Appendix 3](#)).
- Follow-up is also required for non-serious AEs that cause interruption or discontinuation of study treatment and for those present at the end of study treatment as appropriate.
- All identified non-serious AEs must be recorded and described on the non-serious AE page of the CRF (paper or electronic). Completion of supplemental CRFs may be requested for AEs and/or laboratory abnormalities that are reported/identified during the course of the study.

After the initial AE/SAE report, the investigator is required to proactively follow each participant at subsequent visits/contacts. All SAEs, and non-serious AEs of special interest (as defined in [Section 9.2](#)), and AEs (SAEs and non-serious AEs) associated with confirmed or suspected SARS-CoV-2 infection will be followed until resolution, until the condition stabilizes, until the event is otherwise explained, or until the participant is lost to follow-up (as defined in [Section 8.3](#)) or for suspected cases, until SARS-CoV-2 infection is ruled out.

Further information on follow-up procedures is given in [Appendix 3](#).

9.2.4 Regulatory Reporting Requirements for SAEs

- Prompt notification by the investigator to the sponsor of SAEs is essential so that legal obligations and ethical responsibilities towards the safety of participants and the safety of a product under clinical investigation are met.
- An investigator who receives an investigator safety report describing SAEs or other specific safety information (eg, summary or listing of SAEs) from the sponsor will file it along with the IB and will notify the IRB/IEC, if appropriate according to local requirements.

Sponsor or designee will be reporting adverse events to regulatory authorities and ethics committees according to local applicable laws including European Directive 2001/20/EC and FDA Code of Federal Regulations 21 CFR Parts 312 and 320. A suspected, unexpected serious adverse reaction (SUSAR) is a subset of SAEs and will be reported to the appropriate regulatory authorities and investigators following local and global guidelines and requirements.

9.2.5 Pregnancy

If, following initiation of the study treatment, it is subsequently discovered that a participant is pregnant or may have been pregnant at the time of study exposure, including during at least 5 half-lives after product administration, the investigator must immediately notify the BMS Medical Monitor/designee of this event and complete and forward a Pregnancy Surveillance Form to BMS designee within 24 hours of awareness of the event and in accordance with SAE reporting procedures described in [Appendix 3](#).

If the investigator determines a possible favorable benefit/risk ratio that warrants continuation of study treatment, or re-initiation of study treatment, a discussion between the investigator and the BMS Medical Monitor/designee must occur. If, for whatever reason, the pregnancy has ended, confirmed by negative serum pregnancy test, treatment may be resumed (at least 3 weeks and not greater than 6 weeks after the pregnancy has ended), following approvals of participant /sponsor /IRB/EC, as applicable.

Follow-up information regarding the course of the pregnancy, including perinatal and neonatal outcome and, where applicable, offspring information must be reported on the Pregnancy Surveillance Form.

Any pregnancy that occurs in a female partner of a male study participant should be reported to sponsor or designee. In order for sponsor or designee to collect any pregnancy surveillance information from the female partner, the female partner must sign an informed consent form for disclosure of this information. Information on this pregnancy will be collected on the Pregnancy Surveillance Form.

In cases where a study drug can be present in seminal fluid, at exposures sufficient to potentially cause fetal toxicity, and if any sexual activity (e.g. vaginal, anal, oral) has occurred between a male participant and a pregnant WOCBP partner(s), the information should be reported to the Sponsor or designee, even if the male participant has undergone a successful vasectomy. In order for Sponsor or designee to collect any pregnancy surveillance information from the female partner, the female partner(s) must sign an informed consent form for disclosure of this information. Information on the pregnancy will be collected on the Pregnancy Surveillance Form.

9.2.6 Laboratory Test Result Abnormalities

The following laboratory test result abnormalities should be captured on the non-serious AE CRF page or SAE Report Form electronic, as appropriate. Paper forms are only intended as a back-up option when the electronic system is not functioning.

- Any laboratory test result that is clinically significant or meets the definition of an SAE
- Any laboratory test result abnormality that required the participant to have study treatment discontinued or interrupted
- Any laboratory test result abnormality that required the participant to receive specific corrective therapy

It is expected that wherever possible, the clinical rather than laboratory term would be used by the reporting investigator (eg, anemia versus low hemoglobin value).

9.2.7 Potential Drug Induced Liver Injury (DILI)

Wherever possible, timely confirmation of initial liver-related laboratory abnormalities should occur prior to the reporting of a potential DILI event. All occurrences of potential DILIs, meeting the defined criteria, must be reported as SAEs (see [Section 9.2](#) and [Appendix 3](#) for reporting details).

Potential drug induced liver injury is defined as:

- 1) ALT or AST elevation > 3x ULN

AND

- 2) Total bilirubin > 2 times ULN, without initial findings of cholestasis (elevated serum alkaline phosphatase),

AND

- 3) No other immediately apparent possible causes of AT elevation and hyperbilirubinemia, including, but not limited to, viral hepatitis, preexisting chronic or acute liver disease, or the administration of other drug(s) known to be hepatotoxic.

9.2.8 Other Safety Considerations

Any significant worsening noted during interim or final physical examinations, electrocardiogram, x-ray filming, any other potential safety assessment required or not required by protocol should also be recorded as a non-serious or serious AE, as appropriate, and reported accordingly.

